1.0 Objectives

Specific Aim 1. Implement CtP for 20 family members of persons with ADRD in four RHS regions (Phase I). A convergent parallel mixed methods design (quan + QUAL) will be implemented to examine the feasibility, acceptability, and utility of CtP over a 1-month period. Twenty caregivers from four RHS regions who use CtP will be interviewed at 1-month to obtain information and guidance on how CtP is best administered in this service context. Three RHS interventionists will also be interviewed after phase I participants complete CtP. The combination of quantitative and qualitative data from Phase I will offer robust data to refine and further prepare CtP for subsequent evaluation in Phase II.

Specific Aim 2. Evaluate the preliminary efficacy and implementation of CtP (Phase II). By utilizing an embedded randomized controlled evaluation, the second phase of this project will implement the findings of Aim 1 to evaluate CtP. A newly enrolled sample of 100 ADRD caregivers will be randomly assigned to one of two groups: one that receives the CtP with guidance from caregiver support staff and a usual care control. Three- and six-month outcomes will include caregiver self-efficacy and distress; caregiver use of recommended support; and service utilization on the part of persons with ADRD. These findings will provide initial insights into efficacy of CtP as well as the acceptability and utility of CtP over time. The results will also serve as a source of empirical estimates to inform subsequent larger-scale evaluation and translation efforts.

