3.0 Study Endpoints/Events/Outcomes

- 3.1 Primary Endpoint/Event/Outcome: Caregiver self-efficacy
- 3.2 Secondary Endpoint(s)/Event(s)/Outcome(s): Caregiver distress (role captivity, role overload, loss of intimate exchange, depressive symptoms); Use of CtP-recommended services

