4.0 Study Intervention(s)/Interaction(s)

Care to Plan (CtP) is an online care planning tool that provides a succinct and clear overview of various types of ADRD caregiver interventions, administers a brief validated assessment of risk, and generates individualized service recommendations for Alzheimer's disease and related dementia (ADRD) caregivers as well as resources that link users to a selected recommendation. Caregivers will complete the tool with the guidance of a CtP interventionist (Senior Care Navigator/Riverside Health System staff).

PROTOCOL TITLE: Care to Plan: Preliminary Efficacy of a Tailored Resource for Family Members of Persons with Dementia

The interventionist will discuss CtP recommendations with caregivers and help caregivers enroll in a recommended support service if so desired. The online tool is located at: <https://caretoplan.ahc.umn.edu/>. Following completion of CtP assessment and consultation, participants would receive a mailing (or e-mailing) including the recommendations generated by the tool.

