The qualitative and quantitative data available from Phase I will be employed to refine the content and delivery of CtP prior to phase II. In phase II, 100 caregivers of persons with ADRD will be enrolled. Similar to phase I, after receiving a new

PROTOCOL TITLE: Care to Plan: Preliminary Efficacy of a Tailored Resource for Family Members of Persons with Dementia

contact, the UMN team will conduct a telephone-based screening for eligibility, complete consent, and administer the baseline survey. Participants will be randomly assigned in a 1:1 ratio to receive either the CtP intervention or a usual care control condition. The UMN team will generate a random assignment schedule using <http://randomizer.org>. The research staff who will have responsibility for all follow-up data collection will not have access to the random assignment schedule, nor will they be able to determine the next treatment assignment in the sequence. The randomization procedures will ensure both random assignment as well as treatment concealment during data collection and are consistent with CONSORT recommendations. Participants in both groups will be followed for six months with data collection at baseline, three months, and six months. For Phase II, a brief disposition survey to determine the participant's caregiving status, as well as the status of the person they provide care for, will be administered (at 3 and 6 month follow up) prior to administering the appropriate survey. An embedded experimental mixed methods design will be utilized ([QUAN+qual]→qual) that will incorporate various qualitative data collection elements within and following the 6-month randomized controlled evaluation of CtP.

As of February 2021, only those with an ID number (i.e. those reviewing the tool with study interventionists) will have their CaretoPlan responses tracked. Thus, others using the tool for personal use within or outside of the context of the study will no longer have responses tracked. *Note: If it is learned that someone enrolled in the study reviewed the tool on their own prior to reviewing it with a study interventionist, this information will be tracked internally.*

As with phase I, surveys will be administered via telephone or in hard-copy surveys.

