Inclusion criteria will remain the same as detailed in Phase I. Enrollment and recruitment procedures will also largely mirror those of Phase I. As a secondary analytic objective is to examine gender differences in CtP effects (see below), a stratified enrollment process will take place to ensure that at least 1/3 of the Phase II sample are male caregivers. CtP interventionists will be made aware of the recruitment goal of 33 male caregivers and will reach out to them to encourage their participation. If necessary, the study team and RHS will directly engage male caregivers during recruitment and enrollment to further ensure gender representation. Following completion of baseline interviews, caregivers will be randomly assigned to the CtP condition as detailed in Phase I or a usual care control group. The refined CtP with an integrated guide for the coach/navigator will be used to facilitate the use of CtP.

PROTOCOL TITLE: Care to Plan: Preliminary Efficacy of a Tailored Resource for Family Members of Persons with Dementia

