Caregivers of persons with memory loss who contact RHS Senior Care Navigation or other RHS services will likely seek information and support. Senior Care Navigators, social workers, or similar staff will deliver routine care and services to caregivers regardless of: a) whether they decide to enroll in the CtP project; or b) if they are randomly assigned to the control condition. Participants assigned to the usual care control group will be provided with the contact information for Senior Care Navigation. These participants may contact Senior Care Navigation for information and support as desired. Care to Plan enhances standard RHS care by creating a more structured assessment process along with individually tailored recommendations, thus resulting in a more efficient referral process. The time spent using the electronic CtP tool will be tracked. Given the size of the proposed Phase II sample and the number of Care to Plan (CtP) interventionists ($n = 3$), a cluster randomization approach is not feasible. Based on Riverside Health standard practices, individuals may contact Riverside's SCN program for consultation as needed. SCNs will document contact with study participants in both the treatment and usual care groups. Comparisons across treatment and control conditions in the number of interactions with the interventionists (i.e., RHS Senior Care Navigators) will determine if alternative randomization approaches in subsequent, larger-scale evaluations of CtP are necessary.

As indicated in Phase I, a number of approaches will be adopted to examine the degree to which caregivers of persons with ADRD utilize CtP as well as their perceptions of acceptability of the online care planning tool. The time spent using CtP will be tracked, allowing for an analysis of practicality (i.e., how long caregivers actually utilize CtP). Those randomized to receive CtP will also be provided with access to the online tool following review of the tool with a Riverside Health care navigator.

For those completing CtP, the 21-item system review checklist will be administered at 3 to determine how well ADRD caregivers in the treatment group perceive CtP's performance, acceptability, and utility. For those in the treatment group who have not completed CtP by the 3 month time point, follow-up surveys will occur without administration of the review checklist.

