17.0 Data Management

17.1 Data Analysis Plan:

Phase I quantitative analyses: Specific Aim 1. As the Phase I aim is to examine the feasibility, acceptability, and utility of CtP within the partnering RHS sites, the quantitative analyses of the R21 phase will largely rely on descriptive statistics. Specifically, Phase I quantitative analyses will utilize frequency tables and means to examine sample characteristics and item-level responses to the CtP review checklist.

Phase II quantitative analyses: Specific Aim 2. Logistic regression analyses will determine whether participation in the CtP treatment group results in utilization of caregiver support programs over the 6-month evaluation period when compared to ADRD caregivers in the control group. Care to Plan treatment vs. control group membership will be the independent variable of interest; caregiver use of CtP recommended services will serve as the dependent variables.

Additional variables will serve as covariates, including time-invariant and time-varying measurements of stress process covariates. Odds ratios will be examined in order to determine the degree to which these variables explain the observed effects of CtP on dependent variable occurrence. Data available at baseline, 3 months, and 6 months will allow for descriptive and growth curve analyses of rate of change in key outcomes: caregiver efficacy and caregiver distress.^{16,17} The individual growth curve model conceives of development, or change, as the function of an individual growth curve plus random error. In our outcome evaluations, the baseline value will be included as a covariate and time will be “centered” at 6-months post-baseline. We will specifically examine whether individual growth parameter estimates have significant variance around the

PROTOCOL TITLE: Care to Plan: Preliminary Efficacy of a Tailored Resource for Family Members of Persons with Dementia

mean trajectories of change in key dependent variables, and then determine whether treatment group assignment influences outcome change parameters in these models. IBM SPSS 21 will be utilized to conduct the within-subject growth curves; the PI has extensive experience conducting growth curve/trajectory analyses.¹⁸⁻²⁴ An additional advantage of this approach is its ability to incorporate missing longitudinal data points, given assumptions of missing at random.²⁵

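### Use of CtP-recommended services is compared between arms, but as worded only the CtP arm can generally score on it

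*Combined protocol and SAP*

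**What the plan says.** The outcome is worded in three places.

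- Section 3.2 lists it among the secondary outcomes as "Use of CtP-recommended services", without a definition, instrument or scoring rule.
- Section 1.0, Specific Aim 2, names "caregiver use of recommended support" among the three- and six-month outcomes.
- Section 17.1 (Phase II quantitative analyses) first asks whether CtP "results in utilization of caregiver support programs over the 6-month evaluation period when compared to ADRD caregivers in the control group". The next sentence makes treatment group the independent variable and says that "caregiver use of CtP recommended services will serve as the dependent variables".

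The rest of the plan fixes who has recommendations.

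- Section 4.0: the tool "generates individualized service recommendations for Alzheimer's disease and related dementia (ADRD) caregivers".
- Section 5.1, Phase II Procedure: "Following completion of baseline interviews, caregivers will be randomly assigned to the CtP condition" or to usual care. Controls are given contact details for Senior Care Navigation, and "Senior Care Navigators, social workers, or similar staff will deliver routine care and services to caregivers regardless of" enrolment or allocation to control.
- Section 5.1, Waitlist Control: controls are offered the tool after the six-month period, through the extension or by being sent the web address.
- Section 5.1: from February 2021 only users with an ID number, who go through the tool with an interventionist, have their responses stored; "others using the tool for personal use within or outside of the context of the study will no longer have responses tracked".
- Sections 5.1 and 13.4: CtP-arm caregivers who have not completed the tool by three months stay in follow-up and still receive the surveys.

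**The concern.** A between-arm outcome has to be something that a participant in either arm can experience and that is recorded in the same way for both. Read as written, this one is defined by a product of the intervention. A control who starts respite care and a CtP-arm caregiver who starts the same respite care after a CtP recommendation have done the same thing, yet only the second has used a CtP-recommended service.

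The comparison would then show a difference even if CtP changed nobody's use of services. Specific Aim 2 and section 17.2 say that the results are to supply estimates for a larger evaluation, so an odds ratio of this kind could be carried into its planning.

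**Working it through.** The plan states no use rate, sample size or power for this endpoint, so there is no figure to reproduce. The check is a reading of who can score, followed by one conditional illustration.

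**Who can score, as worded**

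| Caregiver | Own CtP recommendations in the six months? | Scoring stated? |
|---|---|---|
| CtP arm, tool completed | Yes, stored under an ID number | No |
| CtP arm, tool not completed | No, unless completed after month 3 | No |
| Control | No, unless the caregiver finds and uses the online tool unaided; since February 2021 those responses are not stored | No |

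A note in section 5.1 adds that an enrolled caregiver's self-directed use before a session with an interventionist is tracked internally if staff learn of it. That records the use, not what was recommended. No section says whether a caregiver without recommendations is scored as a non-user, set to missing, scored against a common list, or given recommendations derived from baseline data.

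**Illustration**

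Inputs from the plan: 100 caregivers and 1:1 allocation (section 5.1) and 10% attrition (section 17.2), so 100 × 0.90 / 2 = 45 per arm.

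Assumed inputs, none of them in the plan: true service use of 40% in both arms (true odds ratio 1), 60% of users choosing a service that CtP recommended, 80% of the CtP arm completing the tool, two-sided 5% Fisher test, no covariates.

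1. *Scored on own recommendations, no control able to score.*
   - CtP arm: 0.40 × 0.60 × 0.80 = 0.192. Control arm: 0.
   - The control odds are 0, so the odds ratio has no finite value.
   - With k of 45 against 0 of 45, the two-sided Fisher p-value is 2 × C(45,k) / C(90,k). For k = 5 it is 2 × 1,221,759 / 43,949,268 = 0.056. For k = 6 it is 2 × 8,145,060 / 622,614,630 = 0.026. The test is therefore significant from six CtP-arm users upward.
   - P(X ≥ 6) for X ~ Binomial(45, 0.192) = 0.887. The expected count is 45 × 0.192 = 8.6.
2. *One common list, scored alike in both arms.*
   - 40% against 40%. Enumerating both binomials exactly, Fisher's test is significant in 3.0% of trials.

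With the same behaviour in both arms, the chance of a significant result is about 89% under one scoring and about 3% under the other.

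**The case against.** The strongest reply is that the harmful reading is not the intended one. Section 17.1 poses its question in arm-neutral terms, as use of caregiver support programs. A logistic comparison with controls presupposes a variable on which controls can score, and the plural dependent variables would fit a set of service types asked of everyone. On that reading CtP-recommended services means the types of service that CtP can recommend, and the problem disappears. The survey forms are held outside this file and may contain such a list. CtP-arm non-completers would then answer the same items as everyone else.

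Much of this stands. The arm-neutral reading is sound and may be the intent. But the sentence that specifies the model's outcome, section 3.2 and Specific Aim 2 all use recommendation-specific wording, and nothing links the two descriptions.

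It is also fair that every rate in the illustration is assumed. It shows what one scoring would do; it does not predict this trial's result.

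A reader might go further and infer that the odds ratio could be biased in either direction. A bias against CtP would need controls to be credited for any service while the CtP arm is credited only for its own list, and no text suggests such a rule. A reader might also infer that the data cannot support a fair comparison. The documents do not show that, because the survey items cannot be seen.

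**Conclusion.** The concern holds for the wording of one secondary endpoint. Followed as written, sections 3.2 and 17.1 define an outcome that depends on assignment, so a difference would arise by construction. This is more than a missing detail, because the literal text gives a comparison that cannot be interpreted.

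Its size depends on the scoring used. Under the stated assumptions it is about 89% significant results with no true effect and no finite odds ratio, against about 3% with a common list. It would be wrong to say that no control could ever have recommendations: the tool is online and a control might use it, though the result would not be stored. Nor is the primary outcome, caregiver self-efficacy, touched, nor the general power statement in section 17.2. Planning estimates for a larger trial are affected only if they are taken from this endpoint.

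**What to change.** In sections 3.2 and 17.1, and in the wording of Specific Aim 2, define the between-arm outcome as use of any service, or of each type, on one fixed list of the service types that CtP can recommend. Score it from the same survey items in both arms at 3 and 6 months. Analyse everyone as randomised, CtP-arm non-completers included. Report uptake of a caregiver's own recommendations descriptively, in CtP-arm tool completers only.

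If the surveys did not put the same items to both arms, report this endpoint descriptively without a between-arm test.

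The cost is a change of wording and, where common items exist, a mapping of those items to the list. The endpoint becomes less specific to CtP's tailoring. If common items do not exist, the between-arm test of this endpoint is lost.

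### Section 17.1 puts time-varying, partly post-randomisation stress measures into the logistic analysis of service use, names no main model, and relies on odds-ratio comparison to explain the CtP effect

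*Combined protocol and SAP*

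**What the plan says.** The Phase II quantitative part of section 17.1 uses logistic regression to establish whether being in the CtP group "results in utilization of caregiver support programs over the 6-month evaluation period". Group membership is the independent variable of interest and use of CtP-recommended services is the dependent variable. A separate paragraph then adds: "Additional variables will serve as covariates, including time-invariant and time-varying measurements of stress process covariates". Its purpose follows: "Odds ratios will be examined in order to determine the degree to which these variables explain the observed effects of CtP". The stress covariates are not listed, by name or by visit.

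On timing, section 5.1 says: "Following completion of baseline interviews, caregivers will be randomly assigned to the CtP condition" or to usual care, and "Participants in both groups will be followed for six months with data collection at baseline, three months, and six months".

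Section 3.2 gives the secondary outcomes as "Caregiver distress (role captivity, role overload, loss of intimate exchange, depressive symptoms); Use of CtP-recommended services". Section 3.1 makes self-efficacy the primary outcome. Section 17.1 assigns self-efficacy and distress to growth curves, and its sentence about including the baseline value as a covariate belongs to that text. No section names a group-only or baseline-adjusted logistic model as the main one.

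**The concern.** Randomisation protects a comparison by group, alone or with covariates fixed before assignment. A covariate measured at 3 or 6 months can itself be changed by CtP or by service use. Conditioning on it can remove part of the CtP effect, or create an association that assignment did not cause.

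Distress is one of the things CtP is tested on, so an effect on stress cannot be assumed away. Service use is counted over the same six months, so the order of stress and use is not fixed either.

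At stake is what the service-use odds ratio means. Two analysts could both follow 17.1 and report different odds ratios, only one of them a randomised comparison. The aim of showing how far stress explains the CtP effect is a mediation question, and 17.1 answers it with a comparison that does not isolate mediation.

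**Working it through.** **1. What is in the model.** Randomisation follows the baseline interview, and surveys are at baseline, 3 and 6 months. A stress measure that varies over these visits therefore includes post-randomisation values. This is inferred, but firmly. The reference to odds ratios ties the covariates to the logistic analysis. The plan gives no rate, effect size or power for service use, so there is no figure of its own to reproduce. All inputs in steps 2 to 4 are assumptions, apart from the 45 per arm in step 4.

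**2. If the covariates are in the treatment-effect model.** Let stress be M = -dT + e, with e of unit variance and T = 1 for CtP. Let logit P(use) = a + bT + cM. Set control use at 40% and choose b so that the total (marginal) odds ratio is 2.00. The adjusted CtP odds ratio is exp(b). Let k = exp|c| be the odds of use per SD of stress.

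| k | d = 0 | d = 0.2, lower stress raises use | d = 0.2, lower stress reduces use | d = 0.5, lower stress raises use | d = 0.5, lower stress reduces use |
|---|---|---|---|---|---|
| 1.5 | 2.06 | 1.89 | 2.23 | 1.68 | 2.52 |
| 2.0 | 2.16 | 1.88 | 2.48 | 1.52 | 3.05 |
| 2.5 | 2.26 | 1.88 | 2.72 | 1.43 | 3.58 |

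The d = 0 column is not bias. It is non-collapsibility, the rise in a logistic odds ratio when any predictive covariate is added. The fair reference for each row is therefore that column, not 2.00. Each other entry is the d = 0 value divided or multiplied by k^d. For k = 2: 2.16 / 2^0.2 = 2.16 / 1.149 = 1.88, and 2.16 × 2^0.5 = 2.16 × 1.414 = 3.05. The part due to conditioning on a measure that CtP has shifted is thus a factor of:

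- 1.5^0.2 to 2.5^0.2, or 1.08 to 1.20, at 0.2 SD;
- 1.5^0.5 to 2.5^0.5, or 1.22 to 1.58, at 0.5 SD.

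Two other links between stress and use:

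- *Use changes stress.* With M = -dT + rY + e (Y = 1 for use), the adjusted odds ratio is 2.00 × exp(rd). For r = -0.5 or +0.5 this gives 1.81 or 2.21 at d = 0.2, and 1.56 or 2.57 at d = 0.5. At d = 0 it stays 2.00. That is the harmless case: CtP reaches stress only through service use and nothing else links the two. It is plausible here, because section 4.0 has the interventionist "help caregivers enroll in a recommended support service if so desired".
- *A shared unmeasured cause U.* In a simulation of 400,000, stress was 0.6 × baseline stress + 0.6 × U + 0.6 × noise, less a CtP effect. The logit of use was -0.85 + 0.3 × baseline stress + 0.6 × U, with no CtP effect on use. With CtP lowering stress by 0.3 or 0.5 units, the baseline-adjusted odds ratio of 1.00 became 1.16 or 1.28 once later stress was added. With no CtP effect on stress it was 0.99. Non-collapsibility does not operate at a true odds ratio of 1, so this shift is bias.

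**3. If the covariates come in a later step.** Take the apparent explained share as 1 - ln(adjusted OR) / ln(2.00).

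- No mediation (d = 0): 2.00 becomes 2.06 to 2.26, a share of -4% to -18%.
- Real mediation, d = 0.2, lower stress raises use: the apparent share is 8% to 9%. The share on the model scale, |c|d / (b + |c|d), is 11% to 22%.
- Stress has no effect on use but shares a cause with it (loading 0.5 or 0.7 on stress, odds ratio 2 per SD on use, opposite signs): 2.00 becomes 1.91 or 1.89 at d = 0.2, a false share of 7% to 8%. At d = 0.5 it becomes 1.73 or 1.64, a false share of 21% to 28%. With the same sign the odds ratio rises instead.

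The comparison can therefore be negative, too small, or positive when nothing is mediated.

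**4. Set against precision.** Section 17.2 has 100 enrolled and 10% attrition, so 45 per arm. With 40% control use (18 of 45) and an odds ratio of 2.00, CtP odds are 0.667 × 2 = 1.333, or 57.1% (25.7 of 45). The standard error of the log odds ratio is √(1/18 + 1/27 + 1/25.7 + 1/19.3) = 0.43, and the 95% interval is 0.86 to 4.63. The shift |c|d is 0.08 to 0.18 at 0.2 SD, under half a standard error. At 0.5 SD it is 0.20 to 0.46, about half to one standard error.

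**The case against.** The best reply is that 17.1 describes a staged analysis. Its first Phase II paragraph is a complete model, with group as exposure and service use as outcome. The additional variables arrive in a new paragraph whose purpose is to explain an effect already observed. This reading is at least as natural as the single-model one, and on it the randomised odds ratio is produced. That stands. A reader might infer that the plan's treatment effect on service use will be biased. The documents do not support so strong a statement, because it needs the single-model reading together with effects of CtP on stress, and links between stress and use, that they do not document.

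It also stands that the illustrations rest on assumed inputs, that part of the movement away from 2.00 is non-collapsibility, and that a small effect on stress would matter little beside the sampling error. This is one secondary outcome in a feasibility-oriented R21. Sections 1.0 and 17.2 speak of supplying estimates for a larger trial in general terms, and neither says the service-use odds ratio will be the planning figure.

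Two further inferences should be resisted. The stress covariates may well overlap with the distress outcomes, but 17.1 does not say so. The primary outcome is analysed by growth curves, so the point does not reach it.

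The reply does not settle two things. The staged reading still leaves no model named as main, and it rests the mechanism question on a comparison that step 3 shows to be unreliable. The next subsection describes its analysis of CtP use and interventionist contact as exploring effects; the service-use paragraph carries no such label.

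**Conclusion.** The point holds on either reading, for different reasons. In one model, the CtP odds ratio need not estimate the effect of assignment if CtP shifts stress other than through service use and the two are otherwise linked. In stages, the randomised odds ratio exists but is not designated, and the odds-ratio comparison mixes mediation with non-collapsibility and confounding.

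Neither the size nor the direction of any bias can be derived from the documents. The worked figures show what could happen if CtP moves stress by 0.2 to 0.5 SD, use odds differ 1.5- to 2.5-fold per SD, and control use is 40%. Severity is minor to moderate.

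**What to change.** In section 17.1:

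1. Name one main service-use model in advance: either group alone, or group plus named covariates measured before randomisation. Choose one, since their odds ratios differ (1.92 against 2.01 at the widest in the simulated scenarios), and report later models against that choice.
2. Label any model containing 3- or 6-month stress measures exploratory and non-randomised. State the mediation method and its assumptions, and use stress measured before the service use it is meant to explain. The schedule may allow this, since section 1.0 says "Three- and six-month outcomes will include caregiver self-efficacy and distress; caregiver use of recommended support": 3-month stress could be set against use between 3 and 6 months, if the surveys date use that way.
3. Replace the sentence on examining odds ratios with a reference to that exploratory analysis.

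The cost is wording only, with no new data. The one downside is that the mechanism question becomes explicitly exploratory.

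### Section 17.1 uses odds ratios to judge how far covariates explain the CtP effect on service use, but odds ratios cannot show that on either reading of the sentence (minor; one secondary outcome)

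*Combined protocol and SAP*

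**What the plan says.** Section 3.2 lists "Use of CtP-recommended services" among the secondary outcomes; the primary outcome is caregiver self-efficacy. For the service-use outcome, section 17.1 states: "Logistic regression analyses will determine whether participation in the CtP treatment group results in utilization of caregiver support programs over the 6-month evaluation period". Treatment arm is the independent variable of interest, and "caregiver use of CtP recommended services will serve as the dependent variables".

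Two further sentences matter here. The first reads "Additional variables will serve as covariates, including time-invariant and time-varying measurements of stress process covariates". The second begins "Odds ratios will be examined in order to determine the degree to which these variables explain the observed effects of CtP".

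The section does not say whether the odds ratios to be examined are the treatment odds ratio with and without covariates or the covariates' own odds ratios. It names no individual covariates and gives no formula, standardised effect or mediation method. Caregiver efficacy and distress are analysed with growth curve models, so this rule does not touch them.

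**The concern.** The second sentence is a rule of inference: odds ratios are to show how much of the CtP effect the covariates account for. The natural reading is a comparison of the treatment odds ratio before and after the covariates enter. In a linear model with a randomised arm, a balanced baseline covariate leaves the treatment coefficient unchanged in expectation. The logistic odds ratio does not behave that way, because it is non-collapsible. The covariate-specific odds ratio lies further from 1 than the marginal one whenever treatment has an effect and the covariate predicts the outcome, even with perfect balance. A covariate on the causal path pulls the other way when its indirect effect has the same sign as the direct effect. The observed change is the net of the two and cannot be read as a share explained.

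On the other reading, a covariate's own odds ratio shows only that it goes with service use. That says nothing about how much of the difference between arms passes through it.

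At stake is a report that stress measures do not explain, or even suppress, the CtP effect when the shift is a property of the scale, or a real indirect effect that goes unseen.

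**Working it through.** The documents give no control rate, odds ratio, covariate strength or power for the logistic analysis, so there is no stated figure to reproduce. The inputs below are assumptions, shown as ranges, except where a section is cited.

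**1. Exact example with a balanced binary covariate.** Split the covariate 50/50 in both arms. Let control risks be 0.20 and 0.80, and let the treatment odds ratio be 3.00 in each stratum.
- Stratum 1: odds 0.25 × 3 = 0.75, risk 0.75/1.75 = 0.4286.
- Stratum 2: odds 4 × 3 = 12, risk 12/13 = 0.9231.
- Averages: control 0.50, CtP (0.4286 + 0.9231)/2 = 0.6758.
- Pooled odds ratio: (0.6758/0.3242)/(0.50/0.50) = 2.08, against 3.00 within strata, with no imbalance.
- Risk difference: crude 0.1758; averaged over strata (0.2286 + 0.1231)/2 = 0.1758. It does not move.

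**2. Normal covariate, same distribution in both arms.** Model: logit P(Y=1) = a + bT + gX, with X ~ N(0,1) independent of arm T. Fix the control risk at 20%, 30% or 50% and the marginal odds ratio at 2.0, then solve for a and b by Gauss-Hermite integration. The true share explained is 0%. Rise in log odds ratio = b/ln 2 − 1.

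| Covariate strength g (logits per SD) | Covariate-adjusted OR | Rise in log OR |
|---|---|---|
| 0.25 | 2.02 | 1.2-1.5% |
| 0.5 | 2.07-2.08 | 5-6% |
| 1.0 | 2.26-2.31 | 18-21% |
| 1.5 | 2.57-2.65 | 36-41% |

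With a treatment odds ratio of 1.0 the shift is zero at every strength. The standardised risk difference is the same with or without X (0.162 at 30% control use).

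**3. A mediator that the odds ratio hides.** Let M = θT + N(0,1) and logit P(Y=1) = a + bT + gM. Set b = ln 2 and g = 1, and choose θ so that the marginal odds ratio is also 2.0. The odds ratio is then 2.0 with and without M, so the apparent share is 0%. At 30% control use:
- θ = 0.139 SD and the CtP risk is 0.4615.
- With the mediator held at its control distribution, the CtP risk is 0.433 (marginal direct odds ratio 1.783).
- Indirect share of the risk difference: (0.4615 − 0.4331)/(0.4615 − 0.30) = 17.6%.
- Indirect share of the marginal log odds ratio: 1 − ln 1.783/ln 2 = 16.6%.

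Across 20-50% control use the hidden share is 16.1-17.6% of the risk difference and 14.7-17.1% of the log odds ratio, so about 15-18%.

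**4. A mediator that is partly hidden.** Take control use 30%, θ = 0.3 and direct conditional odds ratio 2.
- Mediator odds ratio 2 per SD: marginal odds ratio 2.262. The change in odds ratio gives 1 − ln 2/ln 2.262 = 15%, against a true 23% on the marginal log-odds scale.
- Mediator odds ratio 3 per SD: marginal odds ratio 2.285. The change gives 16%, against a true 32%.

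**5. Precision at this sample size.** Section 17.2 gives 100 participants and 10% attrition, and allocation is 1:1, so 100 × 0.9/2 = 45 per arm. Simulation used 1,500 trials per covariate strength, intercept ln(0.3/0.7), conditional treatment odds ratio 2 and a covariate independent of arm.

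| Covariate OR per SD | Mean shift in log OR | Chance SD of shift |
|---|---|---|
| 1.5 | 0.03 | 0.11 |
| 2 | 0.07 | 0.17 |
| 3 | 0.15 | 0.25 |

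The standard error of the log odds ratio itself is about 0.44-0.51. The systematic shift is smaller than its chance variation in every row.

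**The case against.** The plan does not state a before-and-after comparison. That reading is inferred, and no formula, threshold or decision hangs on it. This stands, but the alternative reading, the covariates' own odds ratios, supports a claim of explanation no better.

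The larger distortions need strong covariates. At 30% control use, 1 logit per SD means control risk runs from about 12% to 50% across ±1 SD; 1.5 logits means about 6% to 58%. Nothing in the documents shows that stress measures predict service use this well. This also stands, and it is why the result is given as a range that starts near 1%.

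At 45 per arm, imprecision limits any reading of explanation more than non-collapsibility does. True, but the noise does not rescue the rule. It makes a change in odds ratio still harder to read.

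The same sentences raise a further problem: time-varying covariates may be measured after randomisation and affected by CtP. Adjusting for them can remove part of the total effect on any scale. That is a separate defect. Restricting the model to baseline covariates addresses it, but does not make a change in odds ratio a measure of explanation.

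Finally, an adjusted odds ratio is a legitimate estimate, and a logistic model with baseline covariates still tests validly whether arm affects service use. Both points are accepted; the fault lies in the use made of the odds ratios.

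**Conclusion.** The rule in section 17.1 is unsound on either reading of which odds ratios are meant, and nothing in sections 17.1 or 17.2 corrects it. On the natural reading, the distortion runs from about 1-1.5% of the log odds ratio at 0.25 logit per SD to 36-41% at 1.5 logits. At 1 logit per SD, a mediator carrying about 15-18% of the effect would leave the odds ratio unchanged. These sizes rest on assumed control use of 20-50%, a marginal odds ratio of 2.0, a normally distributed covariate and the covariate strengths shown.

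A reader might infer three stronger things that the documents do not support:
- **That any prognostic covariate distorts the result, so the explanation is wrong by construction.** The shift is zero if CtP has no effect and negligible for weak covariates, and covariate strength is unknown.
- **That the next trial would be mis-sized.** Section 17.2 does aim to produce power estimates, but in a paragraph about growth curve modelling, and it says nothing about carrying odds ratios forward.
- **That the trial's main conclusion is affected.** Efficacy and distress are not analysed by odds ratios.

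Severity is minor: the interpretation of one secondary outcome in a preliminary-efficacy study.

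**What to change.** In section 17.1:
- Delete the sentence that uses odds ratios to judge how far covariates explain the CtP effect.
- Estimate the effect on service use from a logistic model with arm and a named, prespecified set of baseline covariates only.
- Report a standardised risk difference with 95% CI: average the model's predicted risks over all participants under CtP and under usual care, and subtract. An adjusted odds ratio may be reported beside it, labelled as conditional on the covariates.
- If explanation is still wanted, specify an exploratory mediation analysis on the risk-difference scale. Name the mediators and their timing, state the assumptions (including no unmeasured mediator-outcome confounding), and note the low precision at about 45 per arm.

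The cost is a few sentences in the analysis plan and one post-estimation step for the risk difference. No new data are needed.
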